4 CARDIOBAND TR ADJUSTABLE ANNULOPLASTY SYSTEM

4.1 Intended Use

Cardioband TR reconstruction System is indicated for the reconstruction and/or repair of pathological Tricuspid valves.

[figure not shown]
4.2 General Description

The Cardioband Transfemoral (TF) Delivery system is designed to introduce and deploy the Cardioband implant in the appropriate location along the tricuspid annulus and then adjust the Cardioband implant in order to narrow the annulus.

4.2.1 Cardioband Implant

Cardioband implant is an adjustable annuloplasty band designed for valve repair by transfemoral procedure.

The Cardioband implant is deployed and fixated along the anterior - posterior annulus and is then adjusted to remodel the tricuspid valve.

[figure not shown]
The Cardioband implant consists of a contraction wire and polyester fabric covering that are attached to an Adjustment mechanism. The polyester covering is marked with radio-opaque (RO) markers at

set distances along the implant. The Implant guidewire is connected to the adjustment mechanism of each implant in order to enable over-the-wire adjustment after implantation.

4.2.2 The Cardioband Adjustable System

The Cardioband System consists of the following main parts:

1. **Cardioband implant** (Figure 8, Figure 9)
2. **Cardioband Delivery System** (Figure 10) is a transfemoral delivery system, designed to introduce and deploy the Cardioband implant in the appropriate location along the annulus and then adjust the Cardioband implant. The Delivery system consists of the following main parts:
 - a. Transfemoral Steerable Sheath (TSS)
 - b. Dilator, used for introduction of the TSS to the femoral vein and left atrium.
 - c. Implant Delivery System (IDS), which includes a Guide Catheter (GC) and an Implant Catheter.
 - d. Size Adjustment Tool.
3. **Anchor Drives**

For additional details, please refer to Instructions for Use .

	TRI-REPAIR – Tricuspid Regurgitation RePAIR with Cardioband Transcatheter System (TR1-1). Study protocol	
---	---	---

4.4 Justification of the clinical investigation

Currently the best option for Tricuspid regurgitation is repairing the valve with an “annuloplasty ring” in an open heart surgery, usually in concomitant with mitral or other valve repair. Occasionally however the patients are in too high risk for operation, the risk of reoperation is extremely high and has been reported to reach up to 20% mortality ^(32, 33, 3435). Cardioband proposes a non-invasive, fully adjustable, direct annuloplasty repair. The evidence presented above indicates that Cardioband

- 1) lower surgical risks of operation and re-operation by using established transfemoral techniques
- 2) Enable a significant reduction of the mitral septo-lateral annulus, and therefore MR reduction
- 3) Enable fine-tuning of the repair by adjusting the device size on a beating heart per the patient anatomy

Cardioband for treatment of Tricuspid repair targets an unmet clinical need, in that the device is based on established surgical devices, and is expected to allow for treatment of patients that would otherwise not undergo Tricuspid valve repair due to the invasiveness of current techniques. Given these potential benefits, and the favourable safety profile of the Cardioband device for MR repair there is ample justification for a prospective investigation focusing on the clinical performance and safety of the Cardioband system for tricuspid regurgitation valve repair.

5 INVESTIGATION DESIGN & ENDPOINTS

5.1 Clinical Study Overview

This clinical investigation is a single arm, multi-center, prospective study with intra-patient comparisons.

Candidates for Cardioband TR treatment are symptomatic patients with functional tricuspid valve repair. Patients are selected upon clinical conditions and severity of TR. Anatomical feasibility is assessed by Echocardiography and/or other exams (such as CT and angiography) according to the site common practice. Patients will be screened and enrolled according to the study inclusion and exclusion criteria.

Patients will undergo tricuspid valve repair with Cardioband implanted via transcatheter procedure under Transoesophageal / Intracardiac echocardiography (TEE/ICE) and fluoroscopy guidance. Post-procedure clinical care will be performed according to standard management of valve repair; Clinical follow-up including standard post-procedural management of surgical valve repair and Transthoracic Echo (TTE) assessment of the degree of Tricuspid regurgitation will be obtained at hospital discharge, 30 days, 6, 12 and 24 months post-index procedure.

As the follow up at 30 days is of most importance in terms of the patient's safety: The first 3 patients will have to complete 30 days follow up before the recruitment of additional patients. In related to the first 3 patients, recruitment will continue in case of elongated hospitalization or complications that are unrelated to the study device as will be judge by the study clinical event committee.

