9.2 Anticipated risks

The potential risks associated with Cardioband can be divided into three categories: First, there are the risks associated with transcatheter repair procedures the patient population (high risk for surgery) and anaesthesia. These risks are expected to be similar to risks that were reported for mitral valve repair by transcatheter devices in similar populations (e.g. Carillion, mitraclip, etc.). Second, there are the risks uniquely associated with annuloplasty procedures using ring/band which similarly are not expected to significantly differ between marketed systems and the Cardioband System. Third, there are risks specifically associated with the Cardioband procedure. The latter are also expected to be similar to those reported for those reported for the use of Cardioband for mitral repair.

A risk analysis according to ISO 14971 Application of Risk Management to Medical Devices has been conducted.

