9.3 Potential Risks and Adverse Events

The following ANTICIPATED EVENTS have been identified as possible complications of the Cardioband TF procedure:

1. **Risks associated with the procedure and administration of anaesthesia including but not limited to the following:** Death; Stroke/ transient ischemic attack; Haemolysis; Heart block; Perforation or damage of vessels, myocardium or valvular structures; Pericardial

	TRI-REPAIR – Tricuspid Regurgitation RePAIR with CaRdioband Transcatheter System (TR1-1). Study protocol	  
---	---	---

effusion/cardiac tamponade; Haematoma; Blood loss requiring transfusion; Infection including endocarditis and septicaemia; Arrhythmia; Air embolus; Thromboembolism; Fever; Hypertension/hypotension; Allergic dye reaction; Allergic Anaesthesia reactions; Aneurysm; Atrial Septal defect requiring intervention; Arterio-venous fistula; Cardiac Arrest; Coagulopathy; Deep Venous thrombus (DVT); Dyspnoea; Edema; Esophagus irritation; Esophagus perforation or stricture; Gastrointestinal bleeding or infarct; Hematoma; Haemolysis; Haemorrhage requiring transfusion; Infection and pain in insertion or incision site; Lymphatic complication; Mesenteric ischemia; Multi-system failure; Myocardial infarction; Nausea/vomiting; Peripheral ischemia; Prolonged angina; Prolonged ventilation; Pulmonary Congestion; Pulmonary thrombo-embolism; Renal insufficiency; Respiratory failure/atelectasis/pneumonia; septicaemia; Urinary tract infection; Vascular trauma, dissection or occlusion; Vessel spasm; vessel perforation or laceration; worsening heart failure .

2. **Potential risks specifically associated with the use of annuloplasty rings/bands include, but may not be limited to the following:** reoperation and explants; residual or recurrent or worsening regurgitation requiring intervention; haemolysis; conduction system disturbances including atrioventricular block; endocarditis; low cardiac output; right heart failure; failure or degeneration of the natural valvular apparatus due to progression of disease; inadequate repair of the valvular and subvalvular structure; detachment/dislodgment (partial or full) of the annuloplasty ring/band from its site of attachment; migration or malposition; malfunction of the ring/band due to distortion or fracture at the implant or physical or chemical deterioration of band components; bleeding complications related to use of anticoagulant therapy; prosthesis thrombosis; infection.

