10.7 Clinical Events Committee

All Serious adverse events will be reviewed by an independent Clinical event Committee (CEC) for adjudication of the event relation to the study device or procedure. Major SAEs and SAEs that are related or possibly related to device or procedure will be reviewed by all CEC members, other SAEs will be reviewed by the CEC chairperson.

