1.3 Study design

This clinical investigation is a single arm, multi-center, prospective study with intra-subject comparisons. Candidates for Cardioband TR procedure are symptomatic subjects with functional tricuspid valve repair. Subjects are selected upon clinical conditions and severity of TR. Anatomical feasibility is assessed by Echocardiography and/or other exams (such as computerized tomography and angiography) according to the site common practice. Subjects will be screened and enrolled according to the study inclusion and exclusion criteria.

Subjects will undergo tricuspid valve repair with Cardioband implanted via transcatheter procedure under Transoesophageal/Intracardiac echocardiography (TEE/ICE) and fluoroscopy guidance. Post-procedure clinical care will be performed according to standard management of valve repair; Clinical follow-up including standard post-procedural management of surgical valve repair and Transthoracic Echo (TTE) assessment of the degree of Tricuspid regurgitation will be obtained at hospital discharge, 30 days, 6, 12 and 24 months post-index procedure.

As the follow up at 30 days is of most importance in terms of the subject's safety, the first 3 subjects will have to complete 30 days follow up before the recruitment of additional subjects. In relation to the first 3 subjects, recruitment will continue in case of elongated hospitalization or complications that are unrelated to the study device as will be judge by the study clinical event committee.

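### The exception to the first-3-patient recruitment hold tests only for relation to the device, so a serious complication judged procedure-related but not device-related (mainly anaesthesia or TEE harm) would not hold recruitment

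*Protocol*

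**What the plan says.** **The hold.** Protocol 5.1 describes 30-day follow-up as the period that matters most for patient safety. It requires the first 3 patients to finish it before more are recruited.

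**The exception.** The next sentence of Protocol 5.1 says that "recruitment will continue in case of elongated hospitalization or complications that are unrelated to the study device". SAP 1.3 carries the same test and the same judge: "complications that are unrelated to the study device as will be judge by the study clinical event committee". Neither text mentions the procedure.

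**What the CEC decides.** Protocol 10.7 gives the committee the task of "adjudication of the event relation to the study device or procedure". Serious adverse events (SAEs) related or possibly related to either one go to all members.

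**How risks are grouped.** Protocol 9.2 divides the risks into three categories and begins: "First, there are the risks associated with transcatheter repair procedures the patient population (high risk for surgery) and anaesthesia". Item 1 of Protocol 9.3 is headed "Risks associated with the procedure and administration of anaesthesia including but not limited to the following". Its list includes death, "Esophagus irritation; Esophagus perforation or stricture" and "Allergic Anaesthesia reactions".

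**What counts as the device.** Protocol 4.2.2 states: "The Cardioband System consists of the following main parts". The list that follows covers the implant, the transfemoral delivery system (steerable sheath, dilator, implant delivery system, size adjustment tool) and the anchor drives.

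**The concern.** The CEC works with two kinds of attribution, device and procedure, but the exception to the hold uses only one. An event that the committee attributes to the anaesthesia or to TEE guidance, and not to the device, meets the exception as worded.

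That is awkward for an early check in what SAP 1.2 calls an early feasibility study. The patient cannot receive the band without the imaging and sedation that go with it. In the primary safety endpoint (Protocol 5.3.1), death, myocardial infarction, tamponade and stroke count whatever their cause; only cardiac surgery has to be device-related. A procedure-related death in one of the first 3 patients would therefore be a primary safety event, yet it would not hold recruitment if judged unrelated to the device.

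What is at stake is one early pause for review. No estimate or analysis is affected.

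**Working it through.** The plan states no operating characteristic for the hold, so there is no figure to reproduce. The check is a reading of the rule, followed by a short illustration.

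**Step 1. Possible CEC findings and what the rule does with them.**

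| CEC finding | Current wording | With *or procedure* added |
|---|---|---|
| Device-related, or possibly so | Holds recruitment (implied) | Holds recruitment (implied) |
| Procedure-related, not device-related | Does not hold | Holds recruitment |
| Unrelated to both | Does not hold | Does not hold |

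Only the middle row changes. The first row is marked as implied because Protocol 5.1 never states that a device-related complication holds recruitment; this follows only from the exception.

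**Step 2. Two readings of the exception.**

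- Reading A: it waives the 30-day wait. After a procedure-only event, recruitment could go on before 30 days are complete.
- Reading B: the 30-day wait always applies, and the exception only says that such an event does not block recruitment afterwards.

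The text does not choose between them. Under A the event does not keep the wait in force. Under B it adds nothing to a wait that would have happened anyway. Under both, the event itself does not hold recruitment.

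**Step 3. What falls in the middle row.**

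- The sheath, dilator and catheters are part of the Cardioband System (Protocol 4.2.2), and femoral entry is made with that sheath and dilator (Protocol 8.1, step 3).
- Protocol 10.2 counts an event related to use of the device as an adverse device effect, including events from deployment, implantation, operation and use error.
- The exception requires the event to be unrelated, so a possibly device-related event does not qualify.

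Most access, delivery and anchor harm is therefore in the first row. What is left is mainly anaesthesia and TEE harm, plus any access harm not attributed to the system. Protocol 9.3 item 1 names such events.

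**Step 4. Other rules that could act.**

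- Protocol 5.4: the tabulated limits start at 2 events and count only serious adverse device effects, so a procedure-only event does not count.
- Protocol 10.7: a procedure-related SAE is reviewed by the full CEC, but no pause is attached to that review.
- Protocol 10.3.1: German reporting covers SAEs where a causal link to the device, the study or its procedure cannot be excluded. This is notification only.
- Protocol 10.6 and 13.2: the sponsor may suspend or terminate whatever the attribution, on its own judgement.

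None of these is an automatic hold after one procedure-only event.

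**Step 5. Illustration.** Let r be the per-patient probability of a serious procedure-only complication. The documents give no value, so every r below is an assumption, taken as equal and independent across patients. The chance of at least one such event among 3 patients is 1 − (1 − r)³.

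| Assumed r | (1 − r)³ | Chance of at least one in 3 |
|---|---|---|
| 0.5% | 0.9851 | 1.5% |
| 1% | 0.9703 | 3.0% |
| 2% | 0.9412 | 5.9% |
| 5% | 0.8574 | 14.3% |
| 10% | 0.7290 | 27.1% |

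Since the middle row is mainly anaesthesia and TEE harm, nothing in the documents supports the upper end.

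**The case against.** The best defence is that the limitation is deliberate. The study objective is the safety and technical success of the Cardioband system, and Protocol 9.2 expects procedure and anaesthesia risks to resemble those of other transcatheter repair devices. A sponsor can reasonably not want a first-patients check triggered by harm that any such procedure could cause. This stands as an argument about weight: the exception is a defensible choice, and widening it has a price. It does not remove the mismatch with the CEC's remit.

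A second defence is that the gap may be smaller than it looks. Protocol 9.2 introduces all three risk categories as associated with Cardioband, and band adjustment is done under echocardiographic guidance (Protocol 8.1, step 10). The CEC might therefore tie some TEE harm to implantation and so to the device. This also stands in part. It leaves the outcome to case-by-case judgement, which clearer wording would settle.

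Three stronger readings are tempting, and the documents do not support them:

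- A reader might infer that procedural harm in general, including access injury, escapes the hold. The device and adverse-device-effect definitions bring most of it back in.
- A reader might infer that recruitment can certainly go on before 30 days are complete. That is only Reading A; the text fits Reading B as well.
- A reader might infer that a procedure-only event would go unexamined. Full CEC review, the reporting duties and the sponsor's powers all still apply.

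**Conclusion.** The point holds as a minor improvement to wording. Under this rule, a serious complication in the first 3 patients that the CEC judges procedure-related but not device-related would not hold recruitment. That conclusion does not depend on which reading of the exception is right. It does rest on two things: that the CEC would return such a finding, which Protocol 10.7 makes possible, and that device-related complications are meant to hold recruitment, which the text only implies.

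The size is small. The rule covers 3 of up to 60 patients, the events concerned are a narrow class, and other safeguards remain. The percentages show how the chance moves with an assumed rate; they are not an estimate for this trial. The plan contains no numerical error on this point.

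The released documents do not show when the first patients were treated. If they have already completed 30 days, the change matters only for a later protocol that reuses the sentence.

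**What to change.** In Protocol 5.1 and SAP 1.3, extend the exception so that it covers only complications unrelated to the study device *or procedure*, as judged by the CEC. No new assessment is needed, because the committee already adjudicates both relations. Leave the stopping limits in Protocol 5.4 and the ISO-based definitions in Protocol 10.2 as they are.

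While the sentence is open, it would help to say whether the exception waives the 30-day wait or applies once it is over, and to state outright that other complications hold recruitment.

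The cost is a protocol amendment, which under Protocol 11.2 goes to the Competent Authority and back for Ethics Committee approval, and a matching SAP edit. The hold may also apply slightly more often, including for complications that are not specific to this device. Events unrelated to both device and procedure would still not delay enrolment.

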5.2 Study objectives

The objective of this study is to assess the safety and technical success of the Cardioband system for the treatment of symptomatic chronic functional tricuspid regurgitation.

5.3 Study Endpoints

5.3.1 Primary endpoints

Safety:

Overall rate of Major Serious Adverse Events (MSAEs)* and serious adverse device effects (SADE) until hospital discharge and at post-operative 30 days.

* Death, myocardial infarction, cardiac tamponade, device related cardiac surgery, stroke.

Technical Success:

Successful access, deployment and positioning of the Cardioband device and septolateral reduction at intra-procedure and discharge

5.3.2 Secondary endpoints

- TR grade, EROA and Regurgitant Volume (by Echocardiography)
- Tricuspid annular plane systolic excursion (TAPSE)
- Technical success
- NYHA classification
- 6-Minute Walk Distance (6MWD)
- Kansas City Cardiomyopathy Questionnaire (KCCQ)
- LVEF
- LVEDVI
- LVESVI
- NT-pro BNP
- Diuretic Therapy
- GOT, GPT (ALT), and Bilirubin
- BUN Creatinine clearance
- Activity by wearable device

Endpoints will be measured at discharge, 1, 6, 12 and 24 months post procedure and will be compared to baseline

5.4 Study Stopping Criteria

The study will be stopped if in the first 5 patients up to 2 patients will experience one of the following serious adverse device effects:

- Death
- Need for operation/band replacement

The same stopping criteria will be applied to the total study population as it follows:

Device-related SADE and study stopping criteria

SADE	5 pts	10 pts	20	30
Death or need for emergency operation	2	2	3	3

Events will be assessed by an independent clinical event committee (CEC).

In case of early termination of the investigation all the relevant parties will be promptly informed by the sponsor with a report of the reasons of this early termination.

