5.5 Statistical Considerations

5.5.1 Sample size

A sample size of up to 60 patients, enrolled in this proposed multi-center study, is considered adequate to further confirm the safety and performance of the Cardioband System in TR patients. Considerable clinical data on the safety of clinically equivalent devices exists, this will enable a comparison of the clinical data obtained in this study of the safety and performance of the Cardioband System, with literature data from prior studies.

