6.1 Inclusion criteria

Patients who participate in this study must meet all of the following inclusion criteria:

1. chronic functional tricuspid regurgitation (FTR) 2+ to 4+ on a scale of 4+ (moderate to severe) with annular diameter ≥ 40 mm with valve Systolic pulmonary pressure (sPAP) ≤ 60 mmHg
2. ≥ 18 years old
3. New York Heart Association (NYHA) Class II-IVa
4. Symptomatic despite Guideline Directed Medical Therapy (GDMT); at minimum patient on diuretic regimen
5. LVEF $\geq 30\%$
6. Patient is willing and able to comply with all specified study evaluations
7. The Local Site Heart Team concur that surgery will not be offered as a treatment option
8. Transfemoral access of the Cardioband is determined to be feasible

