1.4 Sample size

A sample size of up to 60 patients is considered adequate to further confirm the safety and performance of the Cardioband System in TR patients. Considerable clinical data on the safety of clinically equivalent devices exists. This will enable a comparison of clinical data obtained in this study with literature data from prior studies.

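### Protocol 5.4, the only numeric safety stop, is inconsistent on which events count, does not fix what count triggers it, and has no limit for events in patients 31 to 60

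*Protocol*

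**What the plan says.** Protocol 5.4 opens with a rule for the first 5 patients: the study stops if "up to 2 patients will experience one of the following serious adverse device effects". Two events are listed: death, and "Need for operation/band replacement".

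The rule is then extended: "The same stopping criteria will be applied to the total study population as it follows". The table that follows has one event row, "Death or need for emergency operation", with limits of 2, 2, 3 and 3 under columns for 5, 10, 20 and 30 patients. There is no later column. An independent clinical events committee (CEC) assesses the events.

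On study size, Protocol 5.5.1 says "A sample size of up to 60 patients, enrolled in this proposed multi-center study, is considered adequate", and SAP 1.4 gives the same figure: "A sample size of up to 60 patients is considered adequate to further confirm the safety and performance".

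The other safeguards carry no event limit. Protocol 5.1 pauses recruitment until the first 3 patients have completed 30 days. Protocol 10.7 has the CEC review serious adverse events. Protocol 10.6 and 13.2 let the sponsor terminate or suspend for risk. The SAP contains no stopping rule.

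**The concern.** A numeric stopping rule is useful only if the same events always lead to the same decision. In 5.4 three things needed for that are unsettled: which events are counted, what count triggers the stop, and which patients the limits cover. The documents give no other number to fall back on. What is at stake is the protection of subjects in a study that the SAP calls early feasibility. The endpoint estimates are not affected.

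**Working it through.** **Plan's own figures.** The limits 2, 2, 3, 3 cannot be re-derived. The readable text gives no threshold rate, error rate or target stopping probability for them, and the table in Protocol 5.5.2 is blacked out. The 2-in-5 of the text agrees with the first column of the table. The table in 5.4 shows no redaction mark and has four column headings and four values, so its end at 30 does not look like an extraction loss.

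**Event.** The wordings side by side:

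| Event, device-related | Text of 5.4 | Table of 5.4 |
|---|---|---|
| Death | counts | counts |
| Emergency operation | counts | counts |
| Non-emergency operation or band replacement | counts | does not count |

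Take one device-related death and one non-emergency band replacement in the first 5 patients. The text counts 2; the table counts 1 against a limit of 2. Under the text this is a stop; under the table it is not.

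**Trigger.** Assume each patient independently has a stopping event with probability p, and that all events are known at each look. The documents give no p; 2%, 5% and 10% are assumptions. Let X be the events in the first 10 patients, Y those in patients 11 to 30, and Z those in patients 11 to 60. X, Y and Z are binomial with sizes 10, 20 and 50.

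*Stop when the limit is reached.* The study passes patient 30 only with at most 1 event in the first 10 and at most 2 in the first 30 (these imply passing the looks at 5 and 20):

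P(no stop by 30) = P(X=0)·P(Y≤2) + P(X=1)·P(Y≤1)

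- p = 5%: 0.5987 × 0.9245 + 0.3151 × 0.7358 = 0.5535 + 0.2319, so P(stop) = 0.2146
- p = 10%: 0.3487 × 0.6769 + 0.3874 × 0.3917 = 0.2360 + 0.1518, so P(stop) = 0.6122

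*Stop only when the limit is exceeded.* Every allowance rises by one:

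P(no stop by 30) = P(X=0)·P(Y≤3) + P(X=1)·P(Y≤2) + P(X=2)·P(Y≤1)

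- p = 5%: 0.5987 × 0.9841 + 0.3151 × 0.9245 + 0.0746 × 0.7358 = 0.5892 + 0.2913 + 0.0549, so P(stop) = 0.0645
- p = 10%: 0.3487 × 0.8670 + 0.3874 × 0.6769 + 0.1937 × 0.3917 = 0.3023 + 0.2623 + 0.0759, so P(stop) = 0.3595

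**Scope.** 60 − 30 = 30 planned patients, half of the study, come after the last limit. If no limit applies to them, the stop chance stays at its value for patient 30. If the last limit of 3 is carried to patient 60 and reaching it is enough:

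P(no stop by 60) = P(X=0)·P(Z≤2) + P(X=1)·P(Z≤1)

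- p = 2%: 0.8171 × 0.9216 + 0.1667 × 0.7358 = 0.7530 + 0.1227, so P(stop) = 0.1243
- p = 5%: 0.5987 × 0.5405 + 0.3151 × 0.2794 = 0.3236 + 0.0881, so P(stop) = 0.5883
- p = 10%: 0.3487 × 0.1117 + 0.3874 × 0.0338 = 0.0390 + 0.0131, so P(stop) = 0.9480

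**Summary, chance of a stop:**

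| Assumed rate | By 30, limit reached | By 30, limit exceeded | By 60, no limit after 30 | By 60, last limit carried |
|---|---|---|---|---|
| 2% | 3% | 0.3% | 3% | 12% |
| 5% | 21% | 6% | 21% | 59% |
| 10% | 61% | 36% | 61% | 95% |

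Both columns by patient 60 use the limit-reached reading. Carrying the limit forward is an illustration of the range, not a reading that the protocol states.

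**The case against.** The strongest reply is that subjects are not left unprotected. One independent CEC assesses the events, serious non-emergency device operations still come before it, and the sponsor can stop for risk at any time. All of that stands. But Protocol 10.7 has the CEC adjudicate the relation of an event to device or procedure. Nothing tells it which of the two event wordings triggers the stop, and the sponsor's clauses give no count.

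The gap between the two event wordings may also matter little in practice, because of an inclusion criterion in Protocol 6.1: "The Local Site Heart Team concur that surgery will not be offered as a treatment option". Non-emergency operations may therefore be few. That stands as a limit on the practical effect. It does not remove the conflict, and the text also names band replacement.

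A reader might infer that no number at all can apply once patient 30 is enrolled. The documents do not support that. Section 5.4 states no event window and follow-up runs to 24 months, so late events in the first 30 patients could still meet 3 of 30. What lacks a limit is events in patients 31 to 60.

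A reader might also see a third conflicting definition in the primary safety endpoint of Protocol 5.3.1: "Death, myocardial infarction, cardiac tamponade, device related cardiac surgery, stroke". Those are endpoint components, not stopping events, and the two sets may properly differ.

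**Conclusion.** The concern holds as an inconsistency within Protocol 5.4 and should be fixed. The event definitions in text and table conflict, the trigger is not determined, and the limits do not reach the scope claimed for them. These three conclusions rest on the wording alone and hold at any event rate.

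It is tempting to treat the trigger wording as merely editorial. The size says otherwise: at the 5% and 10% rates the choice between reaching and exceeding the limit moves the chance of a stop by patient 30 by about 15 and 25 percentage points (0.2146 − 0.0645 and 0.6122 − 0.3595). The unstated limit after patient 30 moves the chance by patient 60 by about 37 and 34 points (0.5883 − 0.2146 and 0.9480 − 0.6122).

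These sizes rest on assumed rates, independent patients and events known at each look. The size of the event conflict cannot be given, because the documents do not say what share of stopping events would be non-emergency.

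**What to change.** The sponsor, with the CEC, should amend 5.4 in three places:

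- Reconcile text and table to one event definition.
- Use one trigger wording in both, stating whether the count must reach or exceed the limit.
- Either state the limit that applies to events in patients 31 to 60, or state that the numeric rule ends at 30 and remove the claim that it covers the whole study.

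No threshold and no event definition is proposed here; these are for the sponsor and the CEC to decide.

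The cost is amendment wording. If a limit is added after patient 30, the chance of stopping rises by an amount that depends on the value chosen. In the illustration with the last limit carried forward, it goes from 3% to 12% at an assumed 2% rate and from 21% to 59% at 5%. The documents give no acceptable rate, so whether such a stop would be unwarranted is also for the sponsor and the CEC to judge.
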